6.11 EFFICACY ANALYSES

The general approach for analysis of continuous outcomes will be analysis of covariance (ANCOVA) with multiple imputation for missing data or mixed models for repeated measurements (MMRM) on observed data.

For binary variables, the general approach will be Mantel-Haenszel estimation of risk difference stratified by dialysis organization with or (without) multiple imputation for handling missing data [Mantel, 1959].

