6.11.4.1 Hb value within the target range

All subjects will be defined as either being in target range (10.0 to 11.0 g/dL) in Weeks 20 through 26 (“yes”) or not (“no”), based on at least one Hb value meeting the target range during the visit windows in Weeks 20 through 26. This analysis includes the observed Hb values only.

The same criterion will be used based on the average Hb value during the visit windows in Weeks 20 through 26. To ensure uniformity across all analyses, the missing binary outcomes will be computed from the imputed complete dataset in the primary analysis.

The proportion of subjects within target range will be calculated, 95% CI for the proportions will be reported along with the difference in proportions as well as the odds ratio; a Mantel-Haenszel method stratified by dialysis organization will be used to calculate the 95% CI for the statistics of treatment comparison.

Noninferiority will be evaluated using a 2-sided CI for the difference in proportions. Noninferiority will have been established if the lower limit of the CI is above -15%.

If the lower limit of the 2-sided CI for the difference in proportions is above zero, superiority will have been established and the finding will be interpreted as providing evidence of a higher proportion of subjects being within the target range for vadadustat relative to the control arm.

Secondary evaluation period (Weeks 46 through 52) will be analyzed using the same method.

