6.11.4.4.1 Analysis of Rescue

The number and percentage of subjects receiving rescue by rescue type, treatment group and analysis period will be summarized. Confidence interval will be 95% CI for these proportions along with the difference in proportions as well as the odds ratio. A Mantel-Haenszel test stratified by the dialysis organization will be used to calculate the 95% CI for the statistics of treatment comparison.

Time to first rescue therapy administration by narrow and broad definitions separately will be estimated using the Kaplan-Meier product-limit method and log rank test. Subjects without events will be censored at last dose date. The hazard ratio and corresponding 95% CI for the comparison of vadadustat to Mircera will be estimated using a Cox proportional hazards model, with treatment group, randomization stratification factor (dialysis organization), and baseline Hb as covariates. Kaplan-Meier plots of time to first rescue will be provided.

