6.12.2 Laboratory Data

6.12.2.1 Hb-related Safety Endpoints

Hb-related safety endpoints will be defined using data from the central laboratory. No imputation will be performed for missing data. For each endpoint in [Table 3](#), the proportion of the study group who satisfy the definition and 95% CI for these proportions will be reported along with the difference in proportions as well as the odds ratio; a Mantel-Haenszel method stratified by the dialysis organization will be used to calculate the 95% CI for the statistics of treatment comparison.

Table 3. Hb-related Safety Endpoints from First Dose Date to Last Visit

Variable	Criterion for “Yes”
Hb >11.0 g/dL	Any Hb >11.0 g/dL at any time after Day 1
Hb >12.0 g/dL	Any Hb >12.0 g/dL at any time after Day 1
Hb >13.0 g/dL	Any Hb >13.0 g/dL at any time after Day 1
Hb >14.0 g/dL	Any Hb >14.0 g/dL at any time after Day 1
Hb <7.0 g/dL	Any Hb <7.0 g/dL at any time after Day 1
Hb <8.0 g/dL	Any Hb <8.0 g/dL at any time after Day 1
Hb <9.0 g/dL	Any Hb <9.0 g/dL at any time after Day 1
Hb <10.0 g/dL	Any Hb <10.0 g/dL at any time after Day 1
Hb increase >1.0 g/dL within any 2-week interval	Difference between 2 Hb values within any 2 weeks >1.0 g/dL after Day 1
Hb increase >2.0 g/dL within any 4-week interval	Difference between 2 Hb values within any 4 weeks >2.0 g/dL after Day 1

Note: Subjects without any post-baseline data will be excluded from this analysis.

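### The risk differences for rescue and Hb excursions are stratified by dialysis organization only, while the rescue hazard ratio and the primary model also adjust for baseline Hb

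*SAP*

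**What the plan says.** SAP 6.11 sets the general rule for binary variables: "Mantel-Haenszel estimation of risk difference stratified by dialysis organization". Three sections apply it.

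- **6.11.4.1, target range:** a Mantel-Haenszel "method stratified by dialysis organization will be used to calculate the 95% CI for the statistics of treatment comparison", with a noninferiority margin of -15 percentage points.
- **6.11.4.4.1, rescue proportions:** a "Mantel-Haenszel test stratified by the dialysis organization will be used to calculate the 95% CI".
- **6.12.2.1, Hb excursions:** a Mantel-Haenszel "method stratified by the dialysis organization will be used to calculate the 95% CI".

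Section 6.11.4.4.1 then specifies a Cox model for time to first rescue "with treatment group, randomization stratification factor (dialysis organization), and baseline Hb as covariates". Baseline Hb also enters the Cox model for treatment discontinuation (6.5), the primary ANCOVA (6.11.2) and the MMRM (6.11.2.1). Section 6.14 already defines a baseline Hb split at 10.0 g/dL for subgroups. Randomization is stratified by dialysis organization alone (3.1).

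**The concern.** Entry requires a mean screening Hb of 8.5 to 11.0 g/dL. Some subjects therefore start below the 9.0 g/dL line used for narrow ESA rescue, and others start at the edge of the 11.0 g/dL excursion threshold. The excursion endpoints count any value after Day 1, so early visits contribute before titration can weaken the link with baseline. Baseline Hb is thus a plausible predictor of these outcomes, and the design does not balance it.

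Two things follow. Intervals that ignore a prognostic baseline value are wider than they need be. And section 6.11.4.4.1 would report two rescue effects side by side that handle the same imbalance differently, without giving a reason.

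**Working it through.** **1. Inputs.** From the documents: change SD 1.2 g/dL, 150 subjects per arm, 30% dropout (SAP 3.3); pooled vadadustat against Mircera, so 300 against 150 (6.11.2); entry Hb 8.5 to 11.0; cut at 10.0 (6.14); 16 scheduled post-baseline visits to Week 52 (protocol Table 1). Assumed, because the documents do not give them: the baseline distribution, the slope b of follow-up Hb on baseline Hb, the mean follow-up Hb (9.8 or 10.2) and the within-subject correlation.

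**2. The plan's own figure.** With 105 evaluable per arm, SE = 1.2 × √(2/105) = 0.166. Then 0.75/0.166 − 1.96 = 2.57, a power of 99.5%. This agrees with the stated >90% and confirms that 1.2 is the SD of individual changes. No power is stated for the binary endpoints.

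**3. Slopes compatible with SD 1.2.** If r is the baseline-to-follow-up correlation, Var(change) = Var(B) × (b²/r² − 2b + 1). A baseline of N(10, 0.7) truncated to 8.5–11.0 has SD 0.571, so b²/r² − 2b + 1 = 1.44/0.326 = 4.42. Solving:

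- r = 0.3 gives b = 0.65
- r = 0.5 gives b = 1.21
- r = 0.7 gives b = 1.87

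A slope above 1 means that starting differences widen. That is implausible when doses in both arms are adjusted to Hb, so I used slopes of 0.2 to 1.0.

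**4. One Hb value, change SD 1.2.** The SE ratio is √(1 − R²), where R² is the share of the binary outcome's variance explained by the 10.0 split. Ranges cover both follow-up means.

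| Baseline distribution, slope | <9, <10, >11: R² | SE cut | >12: SE cut | In 10.0–11.0: SE cut |
|---|---|---|---|---|
| Uniform, 0.2 | 0.005–0.008 | 0.3–0.4% | 0.1–0.2% | 0–0.1% |
| Truncated normal, 0.6 | 0.020–0.029 | 1.0–1.5% | 0.4–0.6% | 0.1–0.3% |
| Truncated normal, 1.0 | 0.050–0.072 | 2.5–3.7% | 1.0–1.6% | 0.1–0.6% |
| Uniform, 1.0 | 0.083–0.140 | 4.2–7.3% | 2.3–3.5% | 0.1–0.9% |

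The truncated normal here is centred at 10 with SD 0.6 before truncation.

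**5. Any value over 16 visits.** Truncated N(10, 0.7) baseline, mean follow-up 10.2, within-subject correlation 0.3–0.6:

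- Slopes 0.2–0.6: any Hb >11, 0.3–2.3%; any Hb <9, 0.3–3.0%.
- Slope 1.0: about 5% and 6–7%.

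Across >11, >12, <9 and <8 and slopes 0.2–1.0 the range is roughly 0.3 to 7%.

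**6. What that buys.** A 7% cut equals 1/0.93² = 1.16, or 16% more subjects. A 3% cut equals 1/0.97² = 1.06, or 6%. At an event rate of 0.4 the half-width is 1.96 × √(0.24 × (1/300 + 1/150)) = 9.6 points; 7% off gives 8.9.

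**7. Chance imbalance.** If half the subjects start at ≥10.0 (assumed), the between-arm difference in that share has SD √(0.25 × (1/300 + 1/150)) = 5 points. For a single Hb <9 (truncated normal, slope 1.0, rate 0.27, R² 0.062), the risk gap between baseline strata is √0.062 × √(0.27 × 0.73)/0.5 = 0.22. A one-SD imbalance then moves the risk difference by 0.05 × 0.22 = 1.1 points, against a half-width of 1.96 × √(0.197 × 0.01) = 8.7 points.

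**8. Target range.** At a true rate of 0.4 and 300 against 150, 0.15/0.0490 − 1.96 = 1.10, a power of 86.5%. Even at R² = 0.03, more than the split delivers, power is 87.5%.

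**9. Rescue.** Section 6.11.4.4 defines rescue by recorded reason, any ESA use or transfusion, and Mircera dose increases of 50% or 100%. A simulated Hb threshold does not reproduce that, so no figure is given.

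**The case against.** The strongest reply is that nothing here is an error. Stratifying by the sole randomization factor gives a valid interval. The endpoints are other-efficacy and secondary-safety measures outside the formal primary and secondary tests, and the only noninferiority decision among them, target range, gains about one point of power at most. All of this stands.

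A reader might infer a much larger loss by assuming a baseline-to-follow-up correlation of 0.5 to 0.7. The SAP's change SD does not support that, because it would need slopes above 1. A smaller SD does raise the ceiling. With residual SD 0.95 and slope 1.0 the cut for any Hb >11 or <9 reaches 10–12%, but the change SD is then 0.95, not 1.2. If the influence of baseline fades over 13 to 26 weeks, the same setting gives only 0–3%.

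The remedy also has costs. SAP 6.1 merges a stratum of fewer than 30 into the next larger one, which is clear for three organizations but not for a 3 × 2 grid. Any organization with fewer than 60 subjects must have a cell under 30. Conditioning on a prognostic factor also changes what the odds ratio estimates and need not shrink its standard error.

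What survives is the unexplained difference within 6.11.4.4.1 and a modest gain for one-sided thresholds.

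**Conclusion.** The point holds as a low-cost refinement. The rescue and excursion risk differences omit a baseline value that the SAP uses in its main models and in the rescue hazard ratio. The SE reduction is roughly 0.3 to 7% for one-sided excursions and under 1% for average Hb in 10.0–11.0; for rescue it is unknown. These figures rest on assumed slopes of 0.2–1.0, a change SD of 1.2 and the assumed baseline distributions. A flatter baseline distribution raises the upper end, as the single-value table shows.

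Three stronger readings are not supported. The SAP does not show baseline Hb in every ANCOVA: sections 6.11.4.2 and 6.11.4.3 list no covariates, and the model detail in Appendix A is not visible. The rescue analysis as a whole does not ignore baseline Hb, since time to first rescue is adjusted. And the target-range decision is not materially weakened.

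**What to change.** Amend the SAP before database lock, so that the choice cannot look data-driven.

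- **6.11.4.4.1 and 6.12.2.1:** stratify the Mantel-Haenszel risk difference by dialysis organization × baseline Hb (<10.0, ≥10.0 g/dL). Adjust the general rule in 6.11 to match.
- **6.11.4.1:** apply the same strata to the target-range risk difference, for consistency only.
- **6.1:** state that if an organization-by-baseline cell falls under 30, organizations are merged first and the baseline Hb split is kept.
- **Odds ratio:** leave as planned, or label it as conditional on baseline Hb.

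The cost is one added stratum variable at an existing cut, up to six strata instead of three, and a slightly longer merging rule. The return is a small gain on non-primary endpoints. The primary analysis is untouched.

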5.3 OTHER EFFICACY ENDPOINTS

Other endpoints include the following:

- Proportion of subjects having a Hb value within the target range (10.0 to 11.0 g/dL) during the primary evaluation period (Weeks 20 to 26).
- Proportion of subjects having a Hb value within the target range (10.0 to 11.0 g/dL) during the secondary evaluation period (Weeks 46 to 52).
- Proportion of subjects having average Hb value within the target range (10.0 to 11.0 g/dL) during the primary evaluation period (Weeks 20 to 26)
- Proportion of subjects having average Hb value within the target range (10.0 to 11.0 g/dL) during the secondary evaluation period (Weeks 46 to 52)
- Mean change from baseline and percentage change from baseline in the primary efficacy period (PEP) and secondary efficacy period (SEP) for iron-related parameters
- Proportion of subject receiving rescue by analysis periods.
- Proportion of subjects receiving RBC transfusions by analysis periods.
- Proportion of subjects receiving ESA medication by analysis periods.
- Time to first rescue by narrow and broad (include any rescue, ESA, and RBC respectively)
- Proportion of subjects who received any IV iron therapy by analysis period)
- Mean weekly IV dose elemental iron by analysis period and route of administration
- Mean change in serum glucose and lipid parameters between Baseline and the PEP (Weeks 20 to 26) and SEP (Weeks 46 to 52)
- Mean change in iron metabolism (including iron, hepcidin, ferritin, transferrin saturation [TSAT], total iron binding capacity [TIBC]) between Baseline and the PEP (Weeks 20 to 26) and SEP (Weeks 46 to 52)

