6.11.3 Secondary Efficacy Analyses

The study has one secondary efficacy endpoint which will be analyzed formally only if the primary analysis meets the noninferiority margin.

Mean change in Hb between Baseline (average pretreatment Hb) and the secondary evaluation period (average Hb from Weeks 46 to 52, inclusive) will be analyzed using the same methodology as specified for the primary efficacy endpoint. Evaluation of the average change in Hb will employ the approach described for the primary endpoint assessing Weeks 46 to 52 instead of Weeks 20 to 26.

Sensitivity analyses analogous to those performed for the primary efficacy endpoint will be repeated to assess mean change in Hb from Baseline to Weeks 46 to 52. For ANCOVA models, the analysis period of Weeks 46 to 52 will replace the analysis period of Weeks 20 to 26, and for MMRM, the models will be extended to include analysis period up to week 52. The analysis will be repeated for the vadadustat 900 mg TIW starting dose group vs. Mircera and vadadustat 600 mg starting dose group vs. Mircera as exploratory analyses.

After the non-inferiority for both primary and key secondary endpoints have been established, If the lower limit of the 2-sided 95% confidence interval for the difference between the mean Hb change from baseline to Weeks 20 to 26 in the vadadustat group and the mean Hb change from baseline in the Mircera group is above zero, superiority will have been established and the finding will be interpreted as providing evidence of a greater change from baseline in Hb for vadadustat relative to the control arm. Because the same 95% confidence interval is used to the superiority test, no adjustment for multiplicity is needed.

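### SAP 6.11.4.1 lets noninferiority and superiority be declared on the target-range endpoints, in two periods at an unadjusted 95% level, whether or not the primary test succeeds

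*SAP*

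**What the plan says.** SAP 6.11.4.1 defines two binary outcomes. One is "based on at least one Hb value meeting the target range during the visit windows in Weeks 20 through 26", using observed values only. The other applies the same range to the period-average Hb, with missing outcomes taken from the imputed data of the primary analysis.

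The decision rules follow. The basis is a two-sided interval for the risk difference, and the threshold for success is explicit: "Noninferiority will have been established if the lower limit of the CI is above -15" percent. A second rule covers superiority: "If the lower limit of the 2-sided CI for the difference in proportions is above zero, superiority will have been established". The level is given one paragraph earlier: "a Mantel-Haenszel method stratified by dialysis organization will be used to calculate the 95% CI for the statistics of treatment comparison". The section closes by extending all of this to the later period: "Secondary evaluation period (Weeks 46 through 52) will be analyzed using the same method". Nothing limits the rules to one of the two definitions.

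These endpoints stand in SAP 5.3, below the primary and secondary tiers; one of them is "Proportion of subjects having average Hb value within the target range (10.0 to 11.0 g/dL) during the primary evaluation period (Weeks 20 to 26"). SAP 6.11.3 treats the tier above differently: "The study has one secondary efficacy endpoint which will be analyzed formally only if the primary analysis meets the noninferiority margin". SAP 6.11.4, which introduces the other efficacy analyses, names only the analysis population.

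Protocol 4.4 lists only the version based on having an Hb value in range. It gives no test and no margin.

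**The concern.** The ordering is inverted. The secondary endpoint may be tested formally only once the primary has met its margin, while endpoints ranked below it have free-standing rules for declaring success. Those rules use the same kind of language as the primary rule in SAP 6.11.2. The neighbouring other endpoints (iron parameters in 6.11.4.2, glucose and lipids in 6.11.4.3) get comparisons without any such declaration. The SAP does label analyses exploratory where it means to, for the starting-dose comparisons in 6.11.2.1, 6.11.3 and Section 7, but not here.

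Two things are at stake. A report written to the SAP could say that noninferiority was established on Hb control after the primary noninferiority test failed. In addition, several claims are each made at one-sided 2.5% with nothing controlling the set.

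**Working it through.** **The plan's own figure.** The documents give no power or error rate for the target-range tests. The only related figure is the primary test's power of more than 90% (SAP 3.3: SD 1.2, margin 0.75, 150 per arm, 30% dropout). Evaluable per arm: 150 × 0.7 = 105. SE = 1.2 × √(2/105) = 0.166. Power = Φ(0.75/0.166 − 1.96) = Φ(2.57) = 99.5%. For the combined arms, 210 against 105: SE = 1.2 × √(1/210 + 1/105) = 0.143 and power is 99.9%. The stated figure holds.

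**Error over several claims.** The lower limit of a two-sided 95% interval is a one-sided test at α = 0.025, z = 1.96. With k claims, all false and at the margin:

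- Independent: 1 − (1 − α)^k, so 1 − 0.975² = 4.9% and 1 − 0.975⁴ = 9.6%. The bounds kα are 5.0% and 10.0%.
- Equal correlation ρ: 1 − ∫ φ(x) Φ((z − √ρ·x)/√(1 − ρ))^k dx.

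| Claims | ρ = 0 | ρ = 0.5 | ρ = 0.9 |
|---|---|---|---|
| 2 (average Hb, two periods) | 4.9% | 4.5% | 3.5% |
| 4 (both definitions, two periods) | 9.6% | 7.8% | 4.7% |

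The documents do not give the correlation, hence the range. Superiority after noninferiority on the same interval adds no error within one endpoint; the excess comes from multiple endpoints and periods.

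**Primary fails, target-range claim made.** Assumptions not in the documents: normal period-average Hb, equal SD in both arms, correlation 0.5 between periods, and vadadustat mean 0.75 g/dL lower in both periods (the primary null). Sizes are 210 against 105 up to 300 against 150. The proportion in range is Φ((11 − m)/s) − Φ((10 − m)/s). For m = 10.5 and s = 1.2 it is 32.3% on Mircera and, at m = 9.75, 26.9% on vadadustat: a difference of −5.4 points. Simulated chance that the primary fails and at least one average-Hb noninferiority claim is made:

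| Mircera mean | SD | True difference (points) | Chance |
|---|---|---|---|
| 10.5 | 1.2 | −5.4 | 64–76% |
| 10.5 | 1.0 | −8.7 | 34–43% |
| 10.5 | 0.9 | −11.3 | 17–21% |
| 10.5 | 0.8 | −15.0 | about 5% |
| 10.5 | 0.7 | −20.2 | under 1% |
| 10.2 | 1.2 | −8.9 | 36–46% |
| 10.2 | 1.0 | −13.7 | 8–9% |
| 10.2 | 0.9 | −17.3 | about 2% |

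A repeat run agreed to within 2 percentage points. Where the true difference is at or beyond −15, the chance is about 5% or less. Where it is well above that, the true difference lies inside the margin.

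**The case against.** The strongest reply is that these endpoints are not confirmatory. Protocol 4.4, SAP 5.3 and SAP 6.11.4 all class them as other, and SAP 6.11.3 reserves formal analysis for the secondary endpoint, so a reader could infer that lower tiers are descriptive. That inference is reasonable, but the text of 6.11.4.1 contradicts it: a descriptive analysis needs no margin and no rule for when noninferiority is established.

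A reader might take the 17% to 76% figures in the second table as false-claim rates. They are not. In those rows the true difference is −5.4 to −11.3 points, so noninferiority at −15 points would be true for that endpoint. They show discordance between two endpoints, and a mean change and an in-range proportion can legitimately differ. The largest values also borrow SD 1.2, which the SAP states for the change from baseline, not for period-average Hb.

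A reader might also infer an undeclared departure from the protocol, because SAP Section 7 is silent. Protocol 10.5.4 leaves the analysis of exploratory endpoints to the SAP, and the target-range endpoints have no other analysis section in the protocol. The detail may simply have been delegated. That softens the charge, and it supports the exploratory label that the SAP omits.

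Finally, much of SAP Appendices A and B is redacted, so a precondition there cannot be excluded. The readable text on the average-Hb endpoint gives only Mantel-Haenszel estimation from the imputed data.

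**Conclusion.** The point holds as one of wording and claim control. As written, SAP 6.11.4.1 permits noninferiority and superiority to be declared on lower-tier endpoints after a failed primary test, with no order among the claims.

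For the two average-Hb noninferiority claims, the chance of at least one false claim is 3.5% to 4.9% (bound 5.0%) for correlations from 0.9 down to 0, against 2.5% one-sided for a single claim. If the rule also covers the at-least-one-value version, it is 4.7% to 9.6%. These figures need only the 95% level and an assumed correlation.

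The chance of a target-range claim alongside a failed primary runs from under 1% to about 76%. It depends on an SD and means that the documents do not give, and it measures discordance, not error. The primary test's own error rate is untouched, and nothing here puts the primary conclusion in doubt.

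**What to change.** In SAP 6.11.4.1, delete the two sentences that declare noninferiority and superiority, for both periods. State that the target-range analyses are exploratory, and report the stratified risk difference with a nominal 95% interval and no noninferiority or superiority conclusion.

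If a formal claim is wanted, keep only the average-Hb version and write one complete fixed sequence, stopping at the first failure:

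1. primary noninferiority;
2. secondary noninferiority;
3. in a stated order, Hb-change superiority, and target-range noninferiority and superiority at Weeks 20 to 26 and then at Weeks 46 to 52.

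The place of Hb-change superiority must be stated because SAP 6.11.3 already puts it after the two noninferiority tests at the full level, while 6.11.2 allows it straight after the primary. Leaving it out would create parallel branches at full alpha. Write the 95% level into the decision rule itself and list the formal tests in SAP Section 7.

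The cost is SAP wording only: no data, no subjects, no loss of primary power. What is given up is the freedom to make unconditional claims on endpoints for which the protocol sets no test or margin.
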